2.15.6 Analysis of Safety Variables

Safety will be assessed through the degree of pain/discomfort related to the procedure (universal pain scale) and the collection of Adverse Events throughout the course of the study. For each treatment group these variables will be summarized. The summaries will include the number and percent of patients for each outcome. No statistical comparisons will be performed for any of these variables.

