2.0 PROTOCOL

2.1 Protocol Methodology and Analysis

Methodology:

Subjects are to be enrolled in this clinical study if they are a healthy male or female 18 years of age or older. Up to 50 subjects will be enrolled at 3 study centers. Subjects will be enrolled into 2

groups, Group A for TempSure treatments only and Group B for TempSure and Icon treatments. Randomization will not be required as subjects will only be enrolled in Group B and treated with the Icon device if they present with pigment and/r vascular lesions. Subjects will attend a screening/pre-treatment visit which may be performed on the same day as the treatment visit. Subjects in Group A will receive up to 4 treatments with the TempSure device on the face. Subjects in Group B will receive 2 treatments with just the TempSure device and 2 treatments with both the TempSure and Icon device. Some subjects may be asked to return for an optional 5th treatment (2 – 3 weeks post last treatment) with the Icon device (and/or TempSure device) after the completion of their 4 treatments at the discretion of the Investigator. Subjects may receive a phone call 1 week (1-7 days) after each treatment to record side effects. Subjects will return for follow up visits at 4 and 12 weeks post last treatment for efficacy and side effects assessments. An unscheduled visit or phone call may be performed at any time during the study at the request of the subject or as deemed necessary by the site Investigator.

Analysis:

Upcoming generations are proving to have an interest in non-ablative aesthetic treatments and will drive demand for innovated products, procedures, and practice design.¹ Due to this shift in patient base, practices need to evolve to adapt to the newer generational ideologies. There have been rapid advances in RF technology over the past few years and the nonsurgical treatment using this energy source offers great promise to our aging population.² Radiofrequency technology for the treatment facial wrinkles and skin laxity needs to be further investigated to optimize treatment parameters for safe and effective non-ablative aesthetic treatments.

Relevance:

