2.7 Treatment Procedures

- Prior to treatment 1 only, subjects will be asked to complete a Pre-Treatment 1 Questionnaire.
- The defined study area will be identified and may be marked with a surgical marker.
- Procedures for the TempSure treatment:
 - A neutral pad will be placed on the back in an area determined by the Investigator to maintain standard energy settings and to require less power from the device during the treatment.
 - The subject may be required to wear eye shields at the discretion of the Investigator.
 - Gel will be applied to the treatment area.
 - The handpiece will be placed in contact with the skin.
 - The entire defined treatment area will then be treated by delivering energy to the skin.
 - Temperature will be continuously monitored and recorded during treatment.
- Procedures for the Icon treatment:
 - All operators and subjects will wear appropriate protective eyeglasses during the pulse-light treatments.
 - The Skintel Melanin Reader may be used for objective measurement of the melanin content of skin. The Skintel Reader may provide guidance to help select test spot settings.
 - Test spots will be performed prior to treatment in an area in or close to the treatment area in order to determine safe parameters for treatment.
 - The handpiece will be placed in contact with the skin.
 - The entire defined treatment area will then be treated by delivering adjacent pulses with minimal overlap of 20% or less.

- An air-cooling system may be used during treatment. The air-cooling system allows for the continuous flow of cold air on the treatment area to ease the sensation from the pulse.
- Parameters may be adjusted throughout the treatment to increase subject comfort.
- Subjects will be asked to report the general level of treatment discomfort/pain on a scale of 0 (none) to 10 (maximum intolerable pain).
- Photographs may be taken during treatment.
- The additional treatments will follow the same procedure.
- Subjects will receive up to 4 treatments on the face. Subjects in group B may be asked to return for an optional 5th treatment with the Icon device (and/or TempSure device) at the discretion of the Investigator.

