2.12 Schedule of Visits and Procedures

	Visit #1*	Visit #2 - 5	Treatment Visit*** (Optional)	Call (Optional)	Visit #6	Visit #7
Procedure	Screening and Pretreatment Procedures	Treatment Visits 1-4 (1 - 2 weeks apart)	Treatment Visit #5 (2 - 3 weeks post last treatment)	Phone Call 1 Week Post Each Tx (1-7 Days)	Follow Up 4 Weeks Post Last Tx (+/- 1 Week)	Follow Up 12 Weeks Post Last Tx (+/- 1 Week)
Medical History	X					
Pregnancy Verification**	X	X	X			
Informed Consent	X					
Photographs	X	X	X		X	X
FWSS	X				X	X
Subject Pre-Treatment 1 Questionnaire		X				
Treatment		X	X			
Treatment Discomfort/ Pain Evaluation		X	X			
Subject Post Treatment 1 Questionnaire		X				
PGAIS					X	X
SGAIS					X	X
Subject Follow Up Questionnaire					X	X
Adverse Events Assessment	X	X	X	X	X	X

*Screening and Pretreatment Procedures may occur at the same time as the first Treatment Visit.

**Pregnancy verification required before each treatment only for women of childbearing potential.

***Group B only

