2.14 Adverse Event Recording

All data captured must be supported by the Investigator’s timely assessment and documentation of the adverse event in the case report forms or source documents. All documented adverse events will be reviewed by the Sponsor or designee to determine whether the adverse event meets regulatory reporting requirements and to ensure timely adverse event reporting to meet local and global regulatory requirements. All adverse events must be followed until their resolution.

Adverse Events Pertaining to the TempSure Device:

Mild discomfort during treatment may be experienced by the subject. Typically, the discomfort is temporary and localized within the treatment area. Mild edema (swelling) and erythema (redness) may occur. Initial studies indicate that these side effects typically resolve within 2 to 24 hours.

Other anticipated side effects may include; pain, skin burns, bleeding, scarring, crusting, bruising, infection, itching, prolonged edema (swelling) and erythema (redness), hardness, and nodules. Loss of hair pigment may also occur within and adjacent to the treatment area.

Adverse Events Pertaining to the Icon Device:

Adverse effects can include discomfort/pain, redness, swelling, pinpoint bleeding, skin peeling, itching, scabbing, crusting, purpura, and bruising, which are usually transient and resolve without intervention.

Possible adverse effects include pustules (such as ingrown hairs), skin burns, hypopigmentation, hyperpigmentation, removal or lightening of freckles, scarring, infection and allergic reaction (such as a rash). There is also risk of incidental hair reduction or removal in the treated areas.

People of Middle Eastern and Mediterranean descent and those who have an ill-defined hair line with no obvious transition of the hairline to the face are at a high risk for hair stimulation (paradoxical hair growth).

Adverse Events Pertaining to Gel:

The gel is a water-based gel that may be placed on the skin during the TempSure® treatment. No known adverse events are documented. However, an allergic reaction is always possible when placing a topical gel onto the skin. Allergic reaction may include a mild reaction such as skin redness, irritation, or hives.

Adverse Events Pertaining to Neutral Pad:

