2.15 Statistical Analysis**2.15.1 Hypothesis**

For this study to be considered a success, of pre-treatment images when compared to post treatment (90 day) images will be $\geq 80\%$.

For the additional assessments to be considered a success, the following must be true:

- In cases where the subject's improvement is being graded on a scale, such as the FWSS and GAIS scale, we will test the statistical significance of our results against a hypothetical population that would have no change (average score of 4).
- Subject treatment and clinician usability questionnaires are collected.
- The side effect profile (adverse events) and the average pain score is acceptable to the Physician as it relates to the type of treatment.

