2.15.5 Analysis of Efficacy Variables

Additional efficacy variable is the change from baseline to Visit 7 (12 week follow up visit). Baseline is defined as the last assessment prior to the first treatment. The change from baseline to visits 6 and 7 will be analyzed using a Mixed Model Repeated Measures Analysis of Variance. A pairwise treatment group comparison at visit 7 will be performed using the results of this analysis. If a patient has no post-baseline assessment of the primary efficacy variable it will be assumed that the change from baseline to visit 7 is zero. The changes to visits 6 and 7 will be left as missing. Statistical significance with respect to the treatment group comparison at visit 7 will be declared if the two-sided p-value is < 0.05 . For each treatment group, summaries will be prepared for both the observed assessment and the change from baseline. The summaries will include the sample size, mean, median, standard deviation, minimum, and maximum. The statistical significance of the mean change from baseline for each treatment group will be determined using a paired t-test.

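### By-group safety tables (2.15.6) merge TempSure-only and TempSure plus Icon sessions in Group B, so the tolerability of the combined session is shown nowhere

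*Combined protocol and SAP*

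**What the plan says.** - **Safety summary (2.15.6).** Pain and adverse events are covered by one rule: "For each treatment group these variables will be summarized. The summaries will include the number and percent of patients for each outcome". No statistical comparison of these variables is planned.
- **Success rule for the additional assessments (2.15.1).** One condition is: "The side effect profile (adverse events) and the average pain score is acceptable to the Physician as it relates to the type of treatment". No threshold is given.
- **Groups (2.1).** Subjects are placed in "Group A for TempSure treatments only and Group B for TempSure and Icon treatments". Group A has up to four TempSure treatments. For Group B, "Subjects in Group B will receive 2 treatments with just the TempSure device and 2 treatments with both the TempSure and Icon device".
- **Optional fifth session (2.7, 2.12).** It is for Group B only, at the investigator's discretion, with Icon, TempSure or both.
- **Pain measurement (2.7, 2.12).** "Subjects will be asked to report the general level of treatment discomfort/pain on a scale of 0 (none) to 10 (maximum intolerable pain". The schedule marks this at every treatment visit, so a subject has up to four scores, or five in Group B.
- **Summaries elsewhere (2.15.4, 2.15.5).** Quantitative variables get fuller statistics; for efficacy, "The summaries will include the sample size, mean, median, standard deviation, minimum, and maximum".
- **Relatedness (14.0).** Each event is first to be assessed against the study device. The definitions that follow are introduced as being for TempSure treatments. Icon is not named in that section, although Appendix A records that it was added by amendment.

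**The concern.** The physician is asked for a judgement that refers to the kind of treatment, but the tables are organised by the group a subject belongs to. In Group A the two coincide, because every session is TempSure alone. In Group B they do not. The same subjects contribute both TempSure-only and combined sessions, and one row covers both.

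What is at stake is whether a reader can see how well a session with both devices is tolerated. Section 3.3 states that the study uses a handpiece not yet cleared and that Icon may be used outside its cleared instructions, so that profile is worth having. The same blending affects attribution. If relatedness is rated only to TempSure, an event caused by Icon has no clear place to be recorded as such.

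**Working it through.** The plan states no pain means, standard deviations or event rates, so there is no figure to reproduce. The formulas below follow from the session structure; the values put into them are assumptions.

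**1. Mean pain in Group B.** Let m be the mean score at a TempSure-only session and m + d the mean at a session with Icon. All planned sessions are attended and equally weighted.

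- Four sessions: (2m + 2(m + d))/4 = m + d/2, which is d/2 below the combined session.
- Five sessions, Icon used in the fifth at the same d: m + 3d/5, which is 0.4d below.
- Five sessions, TempSure only in the fifth: m + 2d/5, which is 0.6d below.

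| Assumed d | Four sessions (d/2) | Fifth with Icon (0.4d) | Fifth TempSure only (0.6d) |
|---|---|---|---|
| 0 | 0 | 0 | 0 |
| 1 | 0.5 | 0.4 | 0.6 |
| 2 | 1.0 | 0.8 | 1.2 |
| 3 | 1.5 | 1.2 | 1.8 |
| 4 | 2.0 | 1.6 | 2.4 |

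Example with m = 3 and d = 3: the combined session averages 6, while the Group B mean is 4.5 over four sessions, 4.8 with an Icon fifth session and 4.2 with a TempSure-only fifth session.

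**2. Adverse events in Group B.** Let p1 and p2 be the chance of a given effect after a TempSure-only and a combined session, independent across sessions. The share of patients with the effect at least once over four sessions is 1 − (1 − p1)²(1 − p2)².

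- p1 = 0.10, p2 = 0.40: 1 − 0.81 × 0.36 = 70.8%. By type: 1 − 0.81 = 19.0% and 1 − 0.36 = 64.0%.
- Rates swapped (0.40 and 0.10): the row is again 70.8%, but by type it is 64.0% and 19.0%.
- Equal rates with (1 − p)² = 0.9 × 0.6 = 0.54: the row is 1 − 0.54² = 70.8%, and by type 46.0% and 46.0%.
- Ends of an assumed range: p1 = 0.05, p2 = 0.20 gives 42% (by type 10% and 36%); p1 = 0.20, p2 = 0.60 gives 90% (by type 36% and 84%).

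The same row is compatible with opposite session profiles, so it cannot be assigned to either type.

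**3. Can Group A fill the gap?** No. Its tables give an Icon-free profile but contain no combined session.

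**4. Overlap of expected effects (2.14).** Ten effects are listed for both devices: pain, redness, swelling, burns, bleeding, itching, crusting, bruising, scarring and infection. The nature of an event will therefore often not show which device caused it.

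**5. Can events be placed by preceding session?** Often. The schedule gives "Treatment Visits 1-4 (1 - 2 weeks apart", and for the common TempSure effects "Initial studies indicate that these side effects typically resolve within 2 to 24 hours". Section 2.8 puts the Icon sunburn-like sensation at no more than 72 hours. Flaking of pigmented lesions takes 7 to 21 days and can run past the next session, so it has to be placed by onset.

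**The case against.** **The plan already names the statistic.** This is largely right. Section 2.15.1 says average, and the list in 2.15.6 is not exclusive. A reader might infer that a mean is ruled out, or that the pain criterion cannot be evaluated; the text supports neither. A reader might also infer that the criterion could swing between a subject's average and worst session. It cannot, because the rule says average. The two natural versions, the mean of subject means and the mean of all scores, agree when subjects have equal numbers of sessions. How repeated scores enter the count table is unstated, but that is missing detail an analyst would supply.

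**Type of treatment may simply mean the group.** It may, and then the by-group table answers the rule as written. The combined session would still not be shown.

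**The merge need not hide anything.** At d = 0 the pain mean is unaffected. A reader might infer that event rates are diluted as well, but a patient-level row over four sessions cannot be lower than the row for either type: 71% against 64% in the example. The fault is that the row cannot be assigned, not that it is too low.

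**Section 14 is ambiguous rather than shown to fail.** Also fair. It first refers to the study device, and the definitions themselves speak generically of the investigational product. The case report form is not in the documents, so it may already hold an Icon field. What stands is that the introduction to the definitions names TempSure alone.

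**The consequence is small.** Agreed: no test, threshold or primary endpoint depends on this.

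**Conclusion.** The point holds as one about descriptive safety reporting. Summaries by group alone leave the tolerability of the TempSure plus Icon session unreported, although 2.15.1 refers to the type of treatment and pain and adverse events are already collected at each session. The four-session Group B mean understates combined-session pain by d/2, which is 0 to 2.0 points for an assumed d of 0 to 4. This rests on full attendance, equal weighting and the same d at every Icon session. The event percentages are illustrations under assumed, independent rates. The wording on relatedness to Icon is unclear and worth correcting.

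The reach is limited to the safety tables and one physician judgement on an additional assessment. Type I error, power and the primary image-identification criterion are unaffected. The change is worth making because it is cheap, not because the trial's conclusion depends on it.

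**What to change.** 1. **Pain (2.15.6).** Beside the planned by-group counts, report mean (SD) pain by session type: TempSure only, TempSure plus Icon, and Icon alone if used at a fifth session. Average within subject for each type, then across subjects. This also settles the missing mean and how repeated scores enter it.
2. **Adverse events (2.15.6).** List events descriptively by the type of the preceding session, placed by onset, with subjects exposed to that type as the denominator.
3. **Relatedness (14.0).** Rate relationship to TempSure and to Icon separately.

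**Cost.** Two descriptive tables and, if the form lacks it, one relatedness field. No extra visits are needed.

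**Downsides.** Cells will be small, particularly for Icon alone. The two devices stay inseparable within a combined session, and carry-over from one session to the next is possible. Event capture is uneven: after earlier sessions there is a treatment visit 1 to 2 weeks later, whereas after the last one the phone call is optional and the next scheduled contact is the 4-week visit. Section 2.1 does not fix the order of the Icon sessions, so this unevenness could align with session type. The tables should therefore stay descriptive.

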3.0 RISK ANALYSIS AND MANAGEMENT

3.1 Risk Determination

This device study used in this study does not meet the FDA definition for a Significant Risk Device study per 21 CFR 812.3(m). Therefore, the sponsor determines that this is a non-significant risk device study.

Significant risk device means an investigational device that:

- (1) Is intended as an implant and presents a potential for serious risk to the health, safety, or welfare of a subject;
- (2) Is purported or represented to be for a use in supporting or sustaining human life and presents a potential for serious risk to the health, safety, or welfare of a subject;
- (3) Is for a use of substantial importance in diagnosing, curing, mitigating, or treating disease, or otherwise preventing impairment of human health and presents a potential for serious risk to the health, safety, or welfare of a subject; or
- (4) Otherwise presents a potential for serious risk to the health, safety, or welfare of a subject.

3.2 Risk Management

The Investigator in this clinical trial has been invited to participate based on his/her previous experience with the use of the system and/or similar systems and industry experience. Experience with treatments is the most critical element in managing subject risk in this trial.

In addition, as with any study, there is a risk of bias. Objective evaluation methods may be used in conjunction with subjective evaluation methods when feasible. The value of the compensation to the clinical investigator for conducting the study is not influenced by the study outcome. If photographic results are listed as the primary objective, they are to be evaluated by blinded evaluators who did not partake in the study. If information concerning investigator assessment of improvement or investigator satisfaction is collected, then it is not listed as an objective for the study.

All other known risks will be disclosed to the subject via the informed consent process. Since this is an elective procedure and the subjects are volunteers, it can be assumed that their signature on the informed consent is indicative of their agreement to accept the risks involved.

The risks to the subjects who participate in this study are the same as those for the subject undergoing similar non-ablative radiofrequency treatment. It is possible to have an adverse reaction to the TempSure device use. There may be some side effects that we don't know about yet.

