1.2 Objectives

1. Primary Objective:
 - Photographic evaluation with correct identification of pre-treatment 2D images when compared to the 12 week follow up images performed by three independent reviewers.
2. Assessments:
 - Photographic evaluation with correct identification of pre-treatment 2D images when compared to the 4 week follow up images performed by three independent reviewers.
 - Photographic evaluation with Fitzpatrick Wrinkle Severity Scale (FWSS) grading comparing pre-treatment images to the 4 and 12 week follow up images performed by three independent reviewers.
 - Principle Investigator assessment using the Global Aesthetic Improvement Scale (GAIS) at the 4 and 12 week follow up visit.
 - Subject assessment using the Global Aesthetic Improvement Scale (SGAIS) at the 4 and 12 week follow up visit.
 - Subject Questionnaires
 - Pre-Treatment 1
 - Post Treatment 1
 - Follow Up
3. Safety Objectives:
 - Collection of Adverse Events
 - Collection of Treatment Discomfort/Pain Evaluation

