2.2 Protocol Study Design

This is a prospective, open label, multi-center clinical study to collect efficacy data on the TempSure device and may also collect data on the Icon device.

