2.13 Evaluation Methods

Photographs:

Photographs will be taken at baseline and at the 4 and 12 week follow up visit, and may be taken at eat treatment visit to assess the efficacy and safety of treatment.

Treatment Discomfort/Pain Evaluation:

Subjects will be asked to report the general level of treatment discomfort on a scale of 0 (none) to 10 (maximum intolerable pain) using the universal pain assessment tool (Appendix B)

Fitzpatrick Wrinkle Severity Scale

The Fitzpatrick Wrinkle Severity Scale will be used to evaluate outcomes. Live evaluation will be performed at Baseline and the 4 and 12 week follow up visits. The results will be compared to determine improvement.

Class	Wrinkling	Score	Degree of Elastosis
I	Fine wrinkles	1-3	Mild (fine textural changes with subtly accentuated skin lines)
II	Fine to moderate-depth wrinkles, moderate number of lines	4-6	Moderate (distinct papular elastosis [individual papules with yellow translucency under direct lighting] and dyschromia)
III	Fine to deep wrinkles, numerous lines with or without redundant skin folds	7-9	Severe (multipapular and confluent elastosis [thickened yellow and pallid] approaching or consistent with cutis rhomboidalis)

Subject Treatment Questionnaire:

Subject treatment questionnaires may be collected from each subject to obtain feedback on their treatment experience.

Blinded Evaluation:

Three blinded independent reviewers will perform a photographic evaluation in which they will be asked to identify pre-treatment images when compared to post treatment images. The reviewers will be Board Certified Dermatologists and/or Surgeons and will be chosen based on availability and have relevant clinical experience. They will attend a training session prior to grading.

Physician and Subject Questionnaire:

The Global Aesthetic Improvement Scale (GAIS) ranging from “worse” to “very much improved” will be used to judge the improvement as seen by the subject and Investigator.

Global Aesthetic Improvement Scale Assessment	
Rating	Description
1	Very Much Improved- Optimal cosmetic result in this subject

2	Much Improved- Marked improvement in appearance from the initial condition, but not completely optimal for this subject.
3	Improved- Obvious improvement in appearance from initial condition, but a re-treatment is indicated.
4	No Change- The appearance is essentially the same as the original condition.
5	Worse- The appearance is worse than the original condition.

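### The investigator's unblinded GAIS sits in section 1.2 Objectives (under Assessments) and within the success test for the additional assessments, although section 3.2 controls bias by keeping such ratings out of the objectives

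*Combined protocol and SAP*

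**What the plan says.** Section 3.2 (Risk Management) acknowledges a risk of bias and offers two specific protections for efficacy ratings. Photographic results that form the primary objective go to blinded evaluators outside the study. For the investigator's own ratings it states: "If information concerning investigator assessment of improvement or investigator satisfaction is collected, then it is not listed as an objective for the study".

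Section 1.2 (Objectives) has three items: Primary Objective, Assessments and Safety Objectives. Under Assessments it lists "Principle Investigator assessment using the Global Aesthetic Improvement Scale (GAIS) at the 4 and 12 week follow up visit". Section 2.13 confirms that the scale "will be used to judge the improvement as seen by the subject and Investigator", so it is a rating of improvement of the kind section 3.2 describes.

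Section 2.15.1 (Hypothesis) ties overall study success to the photographic comparison, at 80% or more. It then opens a second list with "For the additional assessments to be considered a success, the following must be true". The first entry names FWSS and GAIS and says "we will test the statistical significance of our results against a hypothetical population that would have no change (average score of 4"). The investigator and subject versions of GAIS are not separated.

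Section 2.2 describes the design: "This is a prospective, open label, multi-center clinical study to collect efficacy data on the TempSure device". Under section 2.1, Groups A and B both receive TempSure.

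**The concern.** A rating that section 3.2 keeps out of the objectives because of bias comes back as part of a success criterion. Nothing else in the design protects it. Every subject is treated, the study is open label, and GAIS asks the rater to judge change from the initial condition, so the rater knows which state follows treatment. No blinded GAIS rater is described.

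Expectation alone can push ratings below 4, and a test against 4 cannot tell that shift from a treatment effect. Section 2.1 says the data are meant to support marketing claims. A report could present a significant investigator GAIS as a met criterion while citing section 3.2 as its bias control.

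**Working it through.** **Text comparison**

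| Section | What it does with the investigator's rating |
|---|---|
| 3.2 | Keeps it off the list of objectives, as a bias control |
| 1.2 | Lists it in the section headed Objectives, under the item Assessments |
| 2.13 | Has the investigator judge improvement; describes blinding only for the photographic review |
| 2.15.1 | Tests GAIS against 4, with no exemption for the investigator, among the conditions for success of the additional assessments |

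The Assessments label softens the conflict between 3.2 and 1.2. It does not touch the role given in 2.15.1.

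**How small a shift would pass**

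The plan has no figure to reproduce here: 2.15.2 gives 50 subjects including departures, with no SD, alpha or power. The following is an illustration.

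Inputs:
- n = 50 (2.15.2). This is a ceiling, since 2.1 says up to 50.
- Null mean of 4 (2.15.1).
- Two-sided 0.05, assumed. Sections 2.15.4 and 2.15.5 state it for other comparisons; none is stated for this test.
- *k* subjects rated 3 (Improved) and all others rated 4 (No Change), assumed.

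*One-sample t-test, k = 4.*
- Mean = (4 × 3 + 46 × 4)/50 = 3.92.
- Variance = [4 × 0.92² + 46 × 0.08²]/49 = 3.68/49 = 0.0751, so SD = 0.274.
- t = (3.92 − 4)/(0.274/√50) = −2.06 on 49 df, p = 0.044.
- Four is the smallest *k* that reaches p < 0.05. It is also the smallest at n = 40 (10%, p = 0.044) and n = 30 (13%, p = 0.043).

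*Exact sign or signed-rank test.* Subjects rated 4 contribute zero differences and drop out. The remaining *k* differences all point one way, so p = 2 × (1/2)^k:
- k = 4: 0.125
- k = 5: 0.0625
- k = 6: 0.031

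Six of 50 (12%) are therefore needed. A large-sample Wilcoxon approximation gives 0.046 at k = 4, but with only four non-zero differences it should not be relied on.

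*Smallest significant mean shift for more spread-out ratings.* Shift = t(0.975, n − 1) × SD/√n, with SD assumed between 0.5 and 1.0:

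| n | SD 0.5 | SD 1.0 |
|---|---|---|
| 50 | 0.14 | 0.28 |
| 30 | 0.19 | 0.37 |

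In each case the shift is a fraction of one grade.

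**The case against.** The best reply is that there is no contradiction. Only the middle item of section 1.2 omits the word objective, and the investigator GAIS sits there. Section 3.2 restricts what is listed as an objective; it says nothing about tests or success roles. This has force on the listing and rules out calling the text a flat contradiction. It does not answer 2.15.1. If a rating can avoid the word objective and still count toward success, the safeguard has little practical effect.

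A second reply is that 2.15.1 is loosely drafted. It says significance will be tested, not that the result must be significant, and the next entry is met merely by collecting questionnaires. That is fair, so the success role is a reading of the text. But the entry stands under the sentence "For the additional assessments to be considered a success, the following must be true", and a report could naturally read it as a criterion.

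A third reply is that the 8% figure depends on a t-test applied to data that are 92% tied. This stands, which is why the result is given as a range up to 12%.

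A reader might also infer that the treating clinician scores GAIS live. The documents do not say so. They do not state that the rater delivers the treatments, and section 2.13 uses the word live for FWSS, not GAIS. *Unblinded* is as far as the text goes.

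**Conclusion.** The point holds as a matter to reconcile among sections 1.2, 2.15.1 and 3.2. An unblinded investigator rating bears on success of the additional assessments, although the protocol presents keeping such ratings out of the objectives as a control on bias. Under the stated assumptions (n = 50, two-sided 0.05, all other subjects rated 4), a one-grade benefit of the doubt in 8% to 12% of subjects, depending on the test, would give a significant result.

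Two stronger readings are tempting and not supported. A reader might infer that the trial's main conclusion is exposed, or that the design lacks the protection 3.2 promises altogether. Overall success rests on the photographic comparison, which three blinded independent reviewers carry out, so that half of the safeguard is in place. The effect is on supportive claims only. A reader might also infer that 3.2 forbids testing the investigator's rating. It does not; descriptive reporting follows its intent, not its wording.

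**What to change.** - **Section 2.15.1:** state that the investigator GAIS is excluded from the assessments that decide success.
- **Section 1.2:** move the investigator GAIS out of the Objectives list, or label it there as supportive and unblinded, reported as number and percent in each grade by group and visit.
- **Subject GAIS:** subjects also know they were treated. Label this rating unblinded wherever its test is reported.
- Keep collecting both ratings, and rest the wrinkle-improvement claim on the blinded photographic assessments.

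If the sponsor prefers to keep the investigator GAIS as a success measure, section 3.2 should be revised to say so and to state how rater bias is controlled.

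The recommended change is wording only, with no new data, visits or subjects. The sponsor loses one p-value from its list of supportive successes.
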